6.2 Appendix 2: Description of Analyses

For each measure, analyses will be presented separately for each originating study and, for AMAM-originating participants will be summarized by intervention group in Study AMAX and intervention received in AMAM (see Section 5.1.4).

		Analysis Method	Population	
Measure	Variable	(Section 5.1.1)	(Section 4)	Time Point(s)
SES-CD	Endoscopic response	Descriptive analysis with NRI, mNRI and as Observed	PAS (primary) mITT (sensitivity) PAS – In participants with endoscopic response at W52 of originating study (sensitivity) PAS – In participants without endoscopic response at W52 of originating study	All visits with measurements in Complete Study Period
	Alternate Endoscopic remission SES- CD ≤ 4	Descriptive analysis with NRI, mNRI and as Observed Descriptive analysis with NRI, mNRI and as Observed	PAS - In participants with endoscopic remission at W52 of originating study PAS - In participants without endoscopic remission at W52 of originating study	All visits with measurements in Complete Study Period All visits with measurements in Complete Study Period
	SES-CD total score	Descriptive analysis with mBOCF and as Observed	PAS – In participants from Study AMAM	All visits with measurements in Complete Study Period

Measure	Variable	Analysis Method (Section 5.1.1)	Population (Section 4)	Time Point(s)
	Change from baseline in SES-CD total score	Descriptive analysis with ANCOVA and as Observed	PAS – In participants from Study AMAM	All visits with measurements in Complete Study Period
CDAI	Clinical remission by PRO	Descriptive analysis with NRI	PAS – In participants with clinical remission by PRO at W52 of originating study PAS – In participants without clinical remission by PRO at W52 of originating study	All visits with measurements in Complete Study Period
		Descriptive analysis with NRI and as Observed	PAS	All visits with measurements in Complete Study Period
	Clinical response by PRO	Descriptive analysis with NRI	PAS – In participants with clinical response by PRO at W52 of originating study PAS – In participants without clinical response by PRO at W52 in originating study	All visits with measurements in Complete Study Period
		Descriptive analysis with NRI as Observed	PAS	All visits with measurements in Complete Study Period
	Clinical remission by CDAI	Descriptive analysis with NRI	PAS – In participants with clinical remission by CDAI at W52 of originating study PAS – In participants without clinical remission by CDAI at W52 of originating study	All visits with measurements in Complete Study Period
		Descriptive analysis with NRI, mNRI and as Observed	PAS	All visits with measurements in Complete Study Period

		Analysis Method	Population	
Measure	Variable	(Section 5.1.1)	(Section 4)	Time Point(s)
	Clinical response by CDAI	Descriptive analysis with NRI, mNRI and as Observed	PAS	All visits with measurements in Complete Study Period
	CDAI total score	Descriptive analysis with mBOCF and as Observed	PAS	All visits with measurements in Complete Study Period
	Change from baseline in CDAI total score	Descriptive analysis with ANCOVA and as Observed	PAS	All visits with measurements in Complete Study Period
	AP average	Descriptive analysis with mBOCF and as Observed	PAS	All visits with measurements in Complete Study Period
	Change from baseline in AP average	Descriptive analysis with ANCOVA and as Observed	PAS	All visits with measurements in Complete Study Period
	SF average	Descriptive analysis with mBOCF and as Observed	PAS	All visits with measurements in Complete Study Period
	Change from baseline in SF average	Descriptive analysis with ANCOVA and as Observed	PAS	All visits with measurements in Complete Study Period
Composite SES-CD and CDAI endpoints	Clinical remission by CDAI and endoscopic response	Descriptive analysis with NRI, mNRI, and as Observed	PAS – In participants with Clinical Remission by CDAI and Endoscopic Response at Week 52 of the Originating study	All visits with measurements in Complete Study Period

		Analysis Method	Population	
Measure	Variable	(Section 5.1.1)	(Section 4)	Time Point(s)
Measure Corticosteroid Free	Corticosteroid free Clinical Remission by CDAI	(Section 5.1.1) Descriptive analysis with NRI, mNRI, and as Observed	PAS – In participants taking corticosteroids at baseline and with CS free clinical remission by CDAI at W52 of originating study PAS – In participants taking	All visits with measurements in Complete Study Period
			corticosteroids at baseline and who did not achieve CS free clinical remission at CDAI at W52 of originating study	
	Corticosteroid free Endoscopic Remission	Descriptive analysis with NRI, mNRI, and as Observed	PAS – In participants taking corticosteroids at baseline and with CS free endoscopic remission by CDAI at W52 of originating study	All visits with measurements in Complete Study Period
			PAS – In participants taking corticosteroids at baseline and who did not achieve CS free endoscopic remission by CDAI at W52 of originating study	

Measure	Variable	Analysis Method (Section 5.1.1)	Population (Section 4)	Time Point(s)
IBDQ	IBDQ total score	Descriptive analysis with mBOCF and as Observed	PAS	All visits with measurements in Complete Study Period
	Change from baseline in IBDQ total score	Descriptive analysis with ANCOVA and as Observed	PAS	All visits with measurements in Complete Study Period
	IBDQ subscores (listed in Appendix 1)	Descriptive analysis with mBOCF and as Observed	PAS	All visits with measurements in Complete Study Period
	Change from baseline for each IBDQ subscore (listed in Appendix 1)	Descriptive analysis with ANCOVA and as Observed	PAS	All visits with measurements in Complete Study Period
	IBDQ response	Descriptive analysis with NRI, mNRI, and as Observed	PAS	All visits with measurements in Complete Study Period
	IBDQ remission	Descriptive analysis with NRI, mNRI, and as Observed	PAS	All visits with measurements in Complete Study Period

Measure	Variable	Analysis Method (Section 5.1.1)	Population (Section 4)	Time Point(s)
EIMs	EIMs presence	Descriptive analysis with NRI	PAS – In participants from Study AMAM with EIMs at baseline	All visits with measurements in Complete Study Period
Fistulae	Fistulae presence	Descriptive analysis with NRI	PAS – In participants from Study AMAM with fistulae at baseline	All visits with measurements in Complete Study Period
	At least 50% reduction in draining fistulae	Descriptive analysis with NRI	PAS – In participants from Study AMAM with fistulae at baseline	All visits with measurements in Complete Study Period
Medical resource utilization and health economics	Crohn's related ER visits count, Hospitalization s count, and Crohn's related surgeries count.	Descriptive analysis with mBOCF and as Observed	PAS	All visits with measurements in Complete Study Period
	Medical resource utilization presence	Descriptive analysis with NRI	PAS	All visits with measurements in Complete Study Period

		Analysis Method	Population	
Measure	Variable	(Section 5.1.1)	(Section 4)	Time Point(s)
Biomarkers	CRP	Descriptive analysis	PAS	All visits with measurements
		with mBOCF and as		in Complete Study Period
		Observed	7.2.7	
	Change from	Descriptive analysis	PAS – In	All visits with measurements
	BL in CRP	with ANCOVA and	participants from	in Complete Study Period
		as Observed	Study AMAM	
			without endoscopic	
			response at W52	
			of originating	
			study	
			PAS – In	
			participants from	
			Study AMAG	
			without	
			endoscopic	
			response at W52	
			of originating	
			study	
	Fecal	Descriptive analysis	PAS – In	All visits with measurements
	calprotectin	with mBOCF and as	participants from	in Complete Study Period
		Observed	Study AMAM	
			without	
			endoscopic	
			response at W52	
			of originating	
			study PAS – In	
			participants from	
			Study AMAG	
			without	
			endoscopic	
			response at W52	
			of originating	
			study	

		Analysis Method	Population	
Measure	Variable	(Section 5.1.1)	(Section 4)	Time Point(s)
	Change from	Descriptive analysis	PAS	All visits with measurements
	BL in Fecal	with ANCOVA and	PAS – In	in Complete Study Period
	calprotectin	as Observed	participants from	
			Study AMAM	
			without	
			endoscopic	
			response at W52	
			of originating	
			study	
			PAS – In	
			participants from	
			Study AMAG	
			without	
			endoscopic	
			response at W52	
			of originating	
			study	
Histology	Histologic	Descriptive analysis	PAS – In	All visits with measurements
	Response	with NRI, mNRI, and	participants with	in Complete Study Period
		as Observed	active histologic	
			disease at baseline	
	Histologic	Descriptive analysis	PAS – In	All visits with measurements
	Remission	with NRI, mNRI, and	participants with	in Complete Study Period
		as Observed	active histologic	
			disease at baseline	
	Histologic	Descriptive analysis	PAS – In	All visits with measurements
	Response and	with NRI, mNRI, and	participants with	in Complete Study Period
	Endoscopic	as Observed	active histologic	
	Response		disease at baseline	
	Histologic	Descriptive analysis	PAS – In	All visits with measurements
	Remission and	with NRI, mNRI, and	participants with	in Complete Study Period
	Endoscopic	as Observed	active histologic	
	Remission		disease at baseline	

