7.1.2. Permanent Discontinuation

Possible reasons leading to permanent discontinuation of study drug include, but are not limited to:

Subject Decision

- The participant requests to discontinue the study drug.

Disease Worsening

- The participant requires treatment with a specified prohibited CD medication (Section 10.7, Appendix 7).
- The participant undergoes surgery for CD (with the exception of drainage of a perianal or other cutaneous abscess or seton placement).

Safety Considerations

- The participant has a diagnosis of any of the following during the study:
 - cancer other than squamous cell or basal cell carcinoma of the skin
 - any colonic adenomatous polyp with low grade dysplasia, not completely removed,
 - any adenomatous polyp with high grade dysplasia
 - evidence of dysplasia in non-polypoid mucosa (indefinite for dysplasia, low grade, or high-grade dysplasia) in the GI tract
 - active TB (Section 8.2.6)
 - HIV/acquired immunodeficiency syndrome (AIDS)
 - hepatitis B or development of detectable hepatitis B virus (HBV) DNA under specified circumstances (Section 8.2.8), or
 - hepatitis C or development of detectable hepatitis C virus (HCV) RNA (Section 8.2.9).
- If the investigator determines that a systemic hypersensitivity reaction has occurred related to study intervention administration, the participant may be permanently discontinued from the study intervention, and the sponsor's designated medical monitor should be notified. If the investigator is uncertain about whether a systemic hypersensitivity reaction has occurred and whether discontinuation of study intervention is warranted, the investigator may consult the sponsor.
- The participant has absolute lymphocyte count $<0.5 \times 10^3/\mu\text{L}$ after retesting (see Section 7.1.3).
- The participant has liver chemistry levels outside acceptable ranges that fail to meet the criteria for resumption of study drug as described in Section 7.1.1.
- The participant becomes pregnant. Pregnant participants will not undergo an endoscopy at the ETV (Section 8.1.1.2).

- Noncompliance with LTBI treatment (see Section 8.2.6).
- The participant has an AE or SAE which, in the opinion of the investigator or sponsor, would preclude the participant from continuing to receive study drug.
- It is recommended that the participant be assessed by an appropriately trained professional to assist in deciding whether the participant is to be discontinued if:
 - CCI [REDACTED]

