9.4.1.4. Missing Data Imputation

While every effort will be made to reduce missing data, the missing data imputation methods described below will be used to assess the efficacy endpoints when participants are permanently discontinued from study drug or otherwise have missing data.

- Nonresponder imputation (NRI): For analysis of categorical efficacy and health outcomes variables, missing data will be imputed using an NRI method. Participants will be considered a Nonresponder for the NRI analysis if they
 - do not achieve the endpoint(s) being analyzed
 - have missing data at the time point of interest that results in nonassessment of (an) endpoint(s) at the time point of interest, or
 - discontinue treatment prior to the time point of interest due to reasons other than participants switching to commercially available mirikizumab or extraordinary circumstances, e.g., inability to supply study drug to a particular region
- Mixed-model for repeated measures: For continuous variables, the analysis may include the MMRM with the missing-at-random assumption for handling missing data. This analysis takes into account both missingness of data and the correlation of the repeated measurements. Additional details will be provided in the SAP.
- Modified Baseline Observation Carried Forward with ANCOVA: For continuous variables, single imputation will be used based on carrying the baseline observation forward. Additional details will be provided in the SAP.

Additional details and sensitivity analyses, including imputed and observed data, will be specified in the SAP.

Methodology to address missing data due to participants switching to commercially available mirikizumab or extraordinary circumstances, e.g., inability to supply study drug to a particular region, will be addressed in the SAP.

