5.1.5 Missing Data Imputation

Intercurrent events (FDA 2017) are events which occur after the study intervention initiation and make it impossible to measure a variable or influence how it should be interpreted. Section 1.1 includes intercurrent events for the primary and secondary endpoints. The missing data methods described below may be used to address the intercurrent event strategies proposed for this study.

Non-Responder Imputation

A hybrid estimand strategy will be used to handle binary endpoints:

- Patients who discontinue study treatment due to reasons other than commercial availability and extraordinary circumstances including study treatment supply issues and the site termination, are categorized as treatment failures after discontinuation. As such, these patients are not considered missing from the perspective of the estimand of interest.
- The hypothetical strategy will be used to handle the ICE of study treatment discontinuation due to commercial availability and extraordinary circumstances including study treatment supply issues and the site termination. Participants with the ICE will be excluded from analysis for timepoints of interest after the ICE. The assumption behind this approach is that measurements after this ICE are missing completely at random and thus the estimation can be implemented using observed values.

^a Unless otherwise specified, these treatment arms are not included in the modeling to estimate treatment effect for MMRM and ANCOVA analysis. Also these treatment arms may be excluded from some tables or figures to simplify the output.

A small number of patients who completed study treatment up to the time point of interest but are sporadically missing the binary endpoint data will still require imputation. These patients will be imputed using NRI.

Modified Baseline Observation Carried Forward (mBOCF)

As a primary analysis for continuous variables, the ANCOVA with mBOCF approach will be used for handling missing data. For continuous endpoints a hybrid estimand strategy is used:

- For ICEs of study intervention discontinuation due to reasons other than commercial
 availability and extraordinary circumstances including study treatment supply issues and
 the site termination, the composite strategy will be used such that measurements after the
 ICEs will return to baseline. As such, these patients are not considered missing from the
 perspective of the estimand of interest.

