			Change from baseline in any one of the IBDQ subscores is defined as IBDQ subscore – baseline IBDQ subscore.	Missing if IBDQ subscore is missing at time point or baseline
		IBDQ response	≥16 point improvement from baseline in IBDQ score as described by Irvine et al. (1996).	Missing if either baseline or observed value is missing.
		IBDQ remission	IBDQ score ≥170 as described by Irvine (2008).	Missing if the IBDQ score is missing

[figure not shown]

Measure	Description	Variable	Derivation / Comment	Definition of missing
Extraintestinal manifestations	EIMs will be collected in the eCRF and include a. arthritis, arthralgia; b. iritis,	EIMs Count	EIMs count will be derived by summing the number of EIMs.	If the question is not answered, it will be
(EIMs)	uveitis; c. erythema nodosum, pyoderma gangrenosum, aphthous, stomatitis.	EIMs Presence	EIMs Count ≥1	missing Missing if EIMs Count is missing
Fistulae	Draining cutaneous and draining rectal/vaginal fistulae will be collected in the eCRF	Number of draining fistulae	Draining fistulae count will be calculated by adding the number of draining cutaneous and rectal/vaginal fistulae.	If the question is not answered, then it will be missing

Measure	Description	Variable	Derivation / Comment	Definition of missing
		Fistulae Presence	Number of draining fistulae ≥1	Missing if number of draining fistulae is missing
		Percent change from baseline in draining fistulae	The percent change reduction will be calculated by subtracting the number of draining fistulae at endpoint from the number of draining fistulae at baseline. The result is divided by the number of draining fistulae at baseline and multiplied by 100.	Missing if number of draining fistulae is missing at baseline or time point.
		At least 50% reduction in draining fistulae	Percent change from baseline in draining fistulae ≥50	Missing if number of draining fistulae is missing at baseline or time point.
Medical resource utilization and health economics	Crohn's related emergency room (ER) Visits, Hospitalizations, Surgeries related to Crohn's disease will be collected in the eCRF.	Crohn's related ER visits count, Hospitalizations count, and Crohn's related surgeries count.	For each participant the number of Crohn's related ER visits, the number of hospitalizations, and the number of Crohn's related surgeries will be calculated during the study.	

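### Non-responder imputation on three endpoints where yes is the bad outcome has no stated direction, and neither it nor baseline carry-forward suits the resource-use endpoints

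*SAP*

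**What the plan says.** SAP Appendix 1 (Section 6.1) derives three binary variables from counts. EIMs presence is an EIM count of at least one. Fistulae presence is "Number of draining fistulae ≥1". Resource-utilization presence is at least one Crohn's-related emergency-room visit, hospitalization or Crohn's-related surgery.

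SAP Appendix 2 (Section 6.2) gives each of them NRI as the only method. The EIM row is restricted to "PAS – In participants from Study AMAM with EIMs at baseline", the fistula row to "PAS – In participants from Study AMAM with fistulae at baseline", and "Medical resource utilization presence" uses the whole primary analysis set (PAS). The underlying emergency-room, hospitalization and surgery counts are assigned "Descriptive analysis with mBOCF and as Observed".

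The imputation rules are in two places. Protocol Section 9.4.1.4 classes as nonresponders those who "do not achieve the endpoint(s) being analyzed", and puts missing data and non-administrative discontinuation in the same class. SAP Section 5.1.5 says that participants who discontinue for such reasons "are categorized as treatment failures after discontinuation". It applies NRI to sporadic gaps and returns continuous measurements to baseline after discontinuation. Those who stop because of commercial availability or extraordinary circumstances are excluded from later time points.

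**The concern.** NRI is conservative when achieving the endpoint is good. Here achieving it is bad, so a rule that scores dropouts as not achieving it scores them as free of the problem. The SAP's failure wording points the other way. Neither document states the code for a presence variable, and these three rows have no as-observed result to show which way the imputation moved the estimate.

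The counts have a separate problem. A rule that returns values to baseline needs a baseline, and these counts accrue during the study. At stake is whether the reported rates of EIMs, draining fistulae and health-care use can be interpreted.

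**Working it through.** The plan states no figure for these endpoints, so there is none to reproduce. The rates below are assumptions.

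**1. Size of the gap between the two codings.** Let p be the presence rate among participants with data, and d the share that NRI covers (non-administrative discontinuation and sporadic gaps).

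- Protocol rule taken literally, dropout coded absent: p(1 − d)
- SAP failure wording, dropout coded present: p(1 − d) + d
- Difference: d, whatever p is

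| Assumed p | Assumed d | Coded absent | Coded present | Gap (points) |
|---|---|---|---|---|
| 10% | 10% | 9% | 19% | 10 |
| 10% | 30% | 7% | 37% | 30 |
| 20% | 20% | 16% | 36% | 20 |
| 40% | 20% | 32% | 52% | 20 |

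In the last row, at an assumed n = 100, the 95% Wilson intervals are 23.7 to 41.7 and 42.3 to 61.5, which do not overlap. The absent coding always lies below the as-observed p, which is the favourable direction.

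**2. Internal check on fistulae.** Appendix 2 also applies NRI to a reduction of at least half in draining fistulae, in the same participants. Take a dropout with b ≥ 1 fistulae at baseline. Coded absent, the later count is 0 and the reduction is 100 × (b − 0)/b = 100%, so the reduction endpoint is met. NRI on that endpoint scores the same person as not meeting it. Only the present coding agrees with it.

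**3. Resource-use presence.** The absent coding makes every NRI-covered participant event-free. The present coding makes every one a user of emergency, hospital or surgical care, whether or not anything happened. Assume d = 25%, a true rate of 15% in those who stay and 40% in those who leave:

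- Truth: 0.75 × 0.15 + 0.25 × 0.40 = 21.3%
- Coded absent: 0.75 × 0.15 = 11.3%
- Coded present: 0.75 × 0.15 + 0.25 × 1 = 36.3%

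Neither recovers the truth.

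**4. Resource-use counts.** Appendix 1 derives them over the study, gives no baseline count and leaves the definition of missing blank. None appears among the visible baseline variables in Appendix 4, where some rows are redacted. The mBOCF value is therefore undefined. If zero were used and replaced what had accrued, then with assumed means of 0.3 events in those who stay and 0.6 before exit in those who leave:

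- Reset to zero, 0.3(1 − d): 0.27, 0.24 and 0.21 at d = 10%, 20% and 30%
- Accrued events kept, 0.3(1 − d) + 0.6d: 0.33, 0.36 and 0.39

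Under the reset, the mean falls as dropout rises.

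**The case against.** A reader might infer that the plan as written biases all these outcomes favourably. The documents do not support that. The SAP's own wording is treatment failure, and the EIM and fistula rows are limited to participants affected at baseline, where failure most naturally means still present. The table specifications are a separate document (SAP Section 1) and may settle the code. For EIMs and fistulae the fault is an unstated direction, not an established bias.

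A reader might also infer that surgery is erased for the very people who had it, because Protocol Section 7.1.2 lists "The participant undergoes surgery for CD" (with exceptions for abscess drainage and seton placement) among the reasons for permanent discontinuation. That is not established either. The SAP rule acts on the period after discontinuation, the surgery comes before it, and Protocol Section 8.10 has sites report hospitalizations and CD surgeries. Nothing instructs anyone to delete an observed event.

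There is also partial cover. The counts have an as-observed analysis, the fistula-reduction endpoint is correctly oriented, and SAP Section 5.6 summarises serious adverse events, which include inpatient hospitalization.

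All of this stands. It does not supply a code for the presence variables or a baseline for the counts. Nor does it rescue resource use, where both codings fail.

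**Conclusion.** The point holds as a defect of specification for EIMs and fistulae, and as an unsuitable method for resource use. Protocol and SAP wording lead to opposite codes for the three presence variables. The literal protocol code is favourable and contradicts the plan's own fistula-reduction result. For resource use, neither NRI coding is valid and mBOCF has no value to return to.

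The gap between codings equals the NRI-covered share, which is algebra. How large that share will be is unknown, because the documents give neither dropout nor event rates; 10 to 30 points is the range for assumed shares of 10% to 30%. The study is descriptive, with no hypothesis test, and the co-primary endpoints are unaffected. This is a minor correction.

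**What to change.** - **EIMs and fistulae.** In participants affected at baseline, define the endpoint as resolution (no EIM; no draining fistula) and then apply NRI, so that dropouts count as not resolved. This agrees with the fistula-reduction endpoint.
- **Resource use.** Drop NRI and mBOCF. Keep every event observed up to and including discontinuation. Report observed events per 100 participant-years, with the proportion of participants having at least one observed event.
- **Exposure.** SAP Section 5.6.1 already plans participant-years for the safety population; the same calculation is needed on the PAS, which these rows use.
- **What to avoid.** Do not recode resource use to no utilization and then apply NRI. That reproduces the present coding: 36.3% against an assumed truth of 21.3% in the example above.

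The cost is a few lines in SAP Appendices 1 and 2 and the recoding of a handful of descriptive variables. No new data collection is needed.
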